Modafinil: Use of modafinil involves a minor increase over minimal risk. Modafinil is generally considered to be safe and well tolerated. The most common adverse reactions (5%) associated with modafinil which occurred more frequently than placebo-treated patients in previous clinical trials were headache, nausea, nervousness, rhinitis, diarrhea, back pain, anxiety, insomnia, dizziness, and dyspepsia. It is recommended that caution be used in patients with a history of psychosis, depression, or mania, to avoid exacerbation of these conditions. Serious rash requiring hospitalization and discontinuation of treatment has rarely been reported. Life-threatening skin conditions such as Steven-Johnson Syndrome or Toxic Epidermal Necrosis Syndrome, angioedema, anaphylaxis, hypersensitivity reactions involving multiple organs, new or increased psychiatric symptoms (including worsening depression, mania, depression, suicidality), or increased blood pressure are possible. Dose reduction is recommended in patients with severe hepatic impairment. Modafinil use may decrease the effectiveness of hormonal contraception, use of alternative or concomitant methods of contraception while taking modafinil and for one month after discontinuation of modafinil treatment is recommended. Elimination of drugs that are substrates for CYP2C19 (e.g., phenytoin, diazepam, propranolol, omeprazole, and clomipramine) may be prolonged by modafinil via inhibition of metabolic enzymes, with resultant higher systemic exposure.

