6.6 Assessment Windows

Day 1 (start of Week 1) is designated as the point at which treatment starts; this will be somewhere between 7 and 14 days after the baseline visit where randomization occurred. The treatment window is the 12 weeks between Day 1 and the end of Week 12.

Efforts will be made to ensure that assessments are gathered as close to the target assessment time points (Week 8, Week 12, and Week 24) as possible; however, unexpected circumstances often arise that make data collection at very specific time points difficult. Therefore, we have established the following assessment windows. If a participant is not able to complete the assessment during the designated assessment window, they will be allowed to stay in the study (at the site investigator discretion), completing any later assessments as they are able and willing.

Protocol deviations will be completed for participants completing the assessments out of window, with the exception of the prescreening to screening assessment window. Protocol deviations will not be reported for self-report survey data. Self-reported survey data at the baseline, 8 week, 12 week and 24 week surveys is not being collected to assess safety-related information (e.g., side effects, AEs). As is standard, participants are not required to answer any self-reported survey questions they do not wish to answer, and some participants opt to skip questions/surveys they are not comfortable with. If participants skip a question(s) on the surveys (administered online via REDCap), they will be prompted by REDCap that they have missed a question(s) and they can go back and answer or choose to proceed without answering. We have found that in previous studies, skipping questions is rare, and thus we do not expect it to affect data validity.

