Additionally, protocol deviations will not be reported for missed EMA assessments administered by the PRO-Diary data during the home monitoring periods. We expect that there may be instances where participants are unable to complete the EMA questions (for example, if it alerts at a time that is inconvenient for them to answer or they forget to answer). Previous studies have shown that compliance with these repeated assessments is ~75%. The EMA assessments do not assess safety so a missed assessment is not a safety concern. We expect that participants will miss some of these assessments and have selected the length of the home monitoring periods (7 days) to make sure data validity is not compromised if participants miss some of the EMA assessments.

Any missed safety assessments will be reported as protocol deviations. Safety assessments are conducted by the coordinator in-person or by phone as applicable under the supervision of the study PIs during the baseline, 8 week, 12 week and 24 week study visits and during any other contact with the participant (e.g., phone calls).

1. Prescreening to Screening/Baseline Assessment Window: Study staff will aim to schedule the screening/baseline visit within 2 weeks of pre-screening. If the baseline visit is beyond 2 weeks from pre-screening, a study staff member will ask prior to the visit if there has been any change (in fatigue, meds, pregnancy, MS relapses, etc.) since pre-screening.
2. Baseline Home Monitoring Assessment Window: Participants will be given 14 days from their Baseline visit to complete their 7-day home monitoring period assessment. Although participants are asked to complete 7 days of home monitoring, a minimum of 3 full days of home monitoring data will be considered adequate (this allows for lost data due to technology malfunction/user error/illness/etc.).
3. Week 8 Assessment Window: A \pm 2-week (\pm 14 days) window around the Week 8 assessment will be considered allowable for data collection, as long as participants have not allowed modafinil treatment to lapse/run out during this time period.

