6.9 SCHEDULE OF ACTIVITIES

Study Activity	Baseline (week -1 to -2)	Weeks 1-7**	Week 8	Weeks 9-11	Week 12	Weeks 13-23	Week 24
Demographics	X						
Medical/Surgical History	X		X		X		X
Interview with a Neurologist for assessment of eligibility	X						
Krupp's Fatigue Severity Scale (FSS)	X						
Patient Health Questionnaire-3	X						
Medication review	X		X		X		X
Baseline urine Pregnancy test if applicable	X						
AE/SAE review (all participants)*	X		X		X		X
Randomization	X						
Modafinil dispensing (for Groups 2 and 3)	X		X				
Study Intervention Administration		X	X	X	X		
Treatment adherence			X		X		
Treatment Utilization Patterns (post-intervention)							X
Excess modafinil destruction (if applicable)					X		
Computer-based self-report measures							
Modified Fatigue Impact Scale (MFIS)	X		X		X		X
EDSS self-report	X						
STOP-BANG questionnaire	X						
RLS Index	X						

Epworth Sleepiness Scale	X		X		X		X
Insomnia Severity Index	X						
Sleep Hygiene Index	X		X		X		X
Patient Health Questionnaire-8	X		X		X		X
Generalized Anxiety Disorder-7	X		X		X		X
Brief Pain Inventory	X		X		X		X
Exercise (Godin)	X		X		X		X
PROMIS Self-Efficacy Scale	X		X		X		X
PROMIS Cognitive Function	X		X		X		X
MSQOL54- Quality of Life Subscale	X		X		X		X
NeuroQoL Ability to Participate in Social Roles & Activities	X		X		X		X
Post-Treatment Questionnaire					X		X
Patient Global Impression of Change					X		X
7-day home monitoring (PRO-Diary) measures							
Physical Fatigue Severity (4x/day)	X				X		
Mental Fatigue Severity (4x/day)	X				X		
Physical Fatigue Impact (4x/day)	X				X		
Mental Fatigue Impact (4x/day)	X				X		
Wake up time (1x/day)	X				X		
Bed time (1x/day)	X				X		
Sleep refreshed (1x/day)	X				X		
Rest breaks (1x/day)	X				X		
Cognitive clarity (1x/day)	X				X		
Cognitive speed (1x/day)	X				X		

Pain Severity (1x/day)	X				X		
Daytime physical activity (continuous)	X				X		

* For Modafinil-treated participants in Group 2 and 3, AE/SAE review will be additionally assessed at the following time intervals:

- 2-4 days after starting Modafinil
- 7-10 days after starting Modafinil

**Activities marked Week 1-7 begin after the baseline assessments, which include a 7-day home monitoring period.

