7.2 Data Collection Technologies

7.2.1 The PRO-Diary

The PRO-Diary is a wrist-worn accelerometer enhanced with a user interface that allows for input of real-time self-reported data. The PRO-Diary will be used in this study to provide optimally sensitive assays of fatigue intensity, fatigue impact, physical activity, and fatigability (calculated using fatigue severity and activity measures). Ratings at wake and bedtime will be initiated by the participant upon waking (not necessarily when they get out of bed) and at bedtime ("lights out" or the time they intend to go to sleep, not necessarily the time they get into bed). An audible alarm will alert participants to use the touch screen to log symptom ratings at 2 times between 11am and 7pm. The PRO-Diary collects physical activity data as 'activity counts' in 15 second epochs during the home monitoring period and stores time-stamped self-report data until the watch is returned to the lab, for data download, cleaning and analysis. The PRO-Diary also generates accelerometer-derived sleep variables, based on physical activity during sleep. These variables include, sleep duration, wake after sleep onset, sleep latency, and sleep efficiency.

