Aim 3: Compare adverse events, side effects, treatment adherence, and patient dropout rates among the three treatment arms and patient subgroups of interest. Descriptive statistics will be used to analyze patterns of adverse events including side effects (incidence, type, severity, and relatedness) and treatment adherence between treatment groups (modafinil vs. CBT vs. combination therapy) throughout the 12-week intervention interval. Adverse event frequency between treatment groups and among subgroups of interest will be evaluated using ANOVA. Multiple linear regression models adjusted for age, gender, EDSS score, baseline fatigue level, baseline activity level, presence of sleep disorder (yes/no), and depression severity (PHQ-8 Score) will be used to determine association between treatment group and treatment adherence (percent usage of prescribed therapy). We also will assess whether degree of treatment effects measured in Aim 1 are related to treatment adherence (e.g. “dose response”).

9.3 Analysis of Exploratory Aims:

Additional analyses modeled as in 9.2 above will also evaluate treatment effect on the difference between 8 week and baseline MFIS scores, to assess whether treatment effects are detectable prior to the 12-week assessment period.

Additional analyses modeled as in 9.2 above will also evaluate treatment effect on the difference between 24 week and baseline MFIS scores, to assess whether treatment effects are detectable following the 12-week assessment period.

Descriptive statistics will be used to summarize clinical treatment utilization patterns between 12-24 weeks, following the 12-week intervention interval.

Analyses modeled as in 9.2 will also be used to evaluate treatment effects on other outcomes at 12 and 24 weeks. We will examine differential treatment effects on changes in the following

factors (assessed via survey): ability to participate in social roles and activities, pain interference, quality of life, and self-efficacy for managing MS symptoms. We will also examine differential treatment effects on changes from baseline to 12 and 24 weeks in the following outcomes that were assessed via survey and/or EMA: pain intensity, perceived cognitive functioning, and pacing behaviors. Treatment group differences in scores on the PGIC measure at 12 and 24 weeks will be examined in models similar to the approach described in 9.2.

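### The Aim 3 harms comparison rests on adverse-event reports with two extra early reviews in the modafinil arms, while PHQ-8, GAD-7 and actigraphy sleep, scheduled alike in all arms, have no harm analysis

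*Combined protocol and SAP*

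**What the plan says.** Section 1.3 lists anxiety and insomnia among the common reactions to modafinil and adds that "new or increased psychiatric symptoms (including worsening depression, mania, depression, suicidality), or increased blood pressure are possible".

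The schedule in section 6.9 places the "Patient Health Questionnaire-8" and the "Generalized Anxiety Disorder-7" at baseline and weeks 8, 12 and 24, with no restriction by arm. The wrist monitor is worn for seven days at baseline and again at week 12. On its sleep output, section 7.2.1 states: "These variables include, sleep duration, wake after sleep onset, sleep latency, and sleep efficiency".

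Section 6.6 says that data from the "surveys is not being collected to assess safety-related information", and of the diary items that "The EMA assessments do not assess safety so a missed assessment is not a safety concern".

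For harms, Aim 3 in section 9.2 plans descriptive statistics over the 12-week intervention period and one test: "Adverse event frequency between treatment groups and among subgroups of interest will be evaluated using ANOVA". The footnote to the section 6.9 schedule gives Groups 2 and 3 two additional adverse-event reviews, at 2-4 and 7-10 days after starting modafinil.

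**The concern.** Comparing harms between arms is a stated aim. For the psychiatric and sleep harms that section 1.3 itself names, the planned comparison uses reported events from participants who know their treatment, and two of the three arms have additional early reviews. An excess of early events in Groups 2 and 3 could then be a drug effect, a result of the extra asking, or both, and the planned ANOVA cannot separate them.

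The trial also collects baseline-anchored measures of the same constructs on one schedule for all arms. These do not depend on how often an arm is asked about side effects. As the plan stands, the report could say nothing about average change in depressive symptoms, anxiety or measured sleep as a possible harm.

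**Working it through.** The plan gives no figure on this point to reproduce. The check sets the sections side by side and counts reviews.

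**1. Harms, measures and planned use**

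| Harm (1.3) | Measure | Schedule, all arms | Role in section 9 |
|---|---|---|---|
| Worsening depression | PHQ-8 | Baseline, weeks 8, 12, 24 | Depression: modifier (Aim 2), covariate for adherence (Aim 3), conditional mediator (9.3) |
| Anxiety | GAD-7 | Baseline, weeks 8, 12, 24 | Anxiety: covariate (Aims 1 and 2), conditional mediator (9.3) |
| Insomnia | Actigraphy sleep duration, latency, wake after sleep onset, efficiency | Baseline, week 12 | Not named; sleep in general is a modifier, covariate or conditional mediator |

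The further outcomes in 9.3 are social participation, pain, quality of life, self-efficacy, cognition, pacing and the global impression of change. Depression, anxiety and sleep are not among them.

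**2. Scheduled adverse-event reviews from treatment start to week 12 (6.9)**

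- Group 1 (CBT): weeks 8 and 12 = 2.
- Groups 2 and 3: days 2-4 and 7-10, plus weeks 8 and 12 = 2 + 2 = 4.
- Adding week 24: 3 versus 5.

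Both extra reviews fall in the first 10 days. For an event that starts after day 10, every arm has the same two scheduled reviews to week 12.

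**3. Why the net imbalance is uncertain**

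Section 7.5 also collects events at any scheduled or unscheduled call, and section 6.6 at any other contact. Groups 1 and 3 have up to 8 + 2 = 10 therapist calls (section 5.3). The documents do not say whether these count as adverse-event contacts. The two extremes are:

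| | Group 1 | Group 2 | Group 3 |
|---|---|---|---|
| No therapist call counts | 2 | 4 | 4 |
| All ten count | 2 + 10 = 12 | 4 | 4 + 10 = 14 |

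Modafinil minus CBT runs from 4 - 2 = +2 to 4 - 12 = -8, so even its sign is open. Combination minus CBT is +2 at both extremes (4 - 2 and 14 - 12).

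**4. Which contrast isolates the drug**

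The CBT sessions in Table 1 cover sleep, thoughts and emotions. A modafinil versus CBT difference on PHQ-8, GAD-7 or sleep therefore mixes CBT benefit with drug harm. In combination versus CBT, both arms have CBT and only one has modafinil.

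**5. How alike the measurements are**

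The schedule is common, but the week 12 timing text is not. Section 6.5 asks Groups 2 and 3 to complete the survey in the last treatment week and says nothing of the kind for Group 1. The week 12 windows in section 6.6 are tied to the last day of modafinil, which Group 1 does not have.

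**The case against.** Four points against the concern have force.

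*Section 6.6 is about deviations.* A reader might infer that the plan forbids safety use of the surveys. It does not. The sentence justifies not reporting missed surveys as deviations and does not mention actigraphy. Deleting it could do harm: the same section makes every missed safety assessment a deviation, so skipped surveys might become reportable.

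*Aim 3 does not rest only on unequal asking.* It also covers adherence and dropout. Reviews at baseline and weeks 8, 12 and 24 are common to all arms, and section 7.5 directs questions at anxiety, insomnia and worsening depressive symptoms. Restricting the comparison to common reviews would therefore check the effect of the extra asking, but the plan does not specify this.

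*The scales are not shown to be more sensitive than event reports.* The documents give no event rates and no SDs for these scales. Suppose, as an assumption, that 10% of one arm and 20% of another worsen by 1 to 2 SD. The mean shift is (0.20 - 0.10) x 1 = 0.1 SD to (0.20 - 0.10) x 2 = 0.2 SD. With 100 per arm, the standard error of a difference is sqrt(1/100 + 1/100) = 0.14 SD, so a mean comparison would detect such a shift poorly. The case for the scales is that they do not depend on how often an arm is asked, not that they have more power. It is also the reason to report proportions worsening beside means.

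*The data are not wholly unused.* The mediation step in 9.3 requires looking at change in mood, anxiety and sleep to week 8. That is a condition for a mediation model, however, not a between-arm harm estimate, and actigraphy is not collected at week 8.

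The measures also have limits. They are taken in unblinded participants, and PHQ-8 and GAD-7 look back two weeks. Actigraphy covers only baseline and week 12. PHQ-8 omits the suicide item. Early transient events would be missed, so these analyses can only be supportive.

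**Conclusion.** The concern holds in limited form. Three measures that match harms named in section 1.3 are scheduled alike in all arms and have no between-arm harm analysis. The adverse-event comparison that carries this part of Aim 3 has four scheduled reviews to week 12 in Groups 2 and 3 against two in Group 1, with no allowance in the analysis.

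A reader might go further and infer that the comparison is biased against modafinil by a calculable amount. The documents do not support that. The extra reviews bear only on events present in about the first 10 days, other contacts may offset or reverse the imbalance for modafinil versus CBT, and no detection or event rates are given.

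This is a low-cost improvement to the analysis plan. It does not invalidate Aim 3. It rests on reading sections 9.2 and 9.3 as the full list of planned analyses.

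**What to change.** 1. In section 9.2, Aim 3, pre-specify as supportive harm analyses the change from baseline by arm in PHQ-8 and GAD-7 at weeks 8 and 12, with week 24 labelled as post-treatment follow-up. Do the same at week 12 for actigraphy sleep duration, latency, wake after sleep onset and efficiency. Report estimates with 95% confidence intervals.
2. Name combination versus CBT as the main drug-harm contrast. If modafinil versus CBT is shown, state that it mixes CBT benefit with drug harm.
3. Report the proportion per arm moving to a worse PHQ-8 or GAD-7 category. State the cut-point values, since section 7.1.2 mentions cut-points without giving them.
4. Add an adverse-event comparison limited to the reviews common to all arms.
5. Keep the deviation rule in section 6.6 and add a clause saying that it does not exclude these scales from the harm analysis.

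The cost is a few model runs, one table and a few sentences. No data collection or participant management changes. The downside is a few more exploratory comparisons on largely self-reported, unblinded data.

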2.2.2 Secondary Outcomes

Changes between 12 weeks and baseline in fatigue intensity, fatigue impact, and fatigability (measured using PRO-Diary ecological momentary assessment and accelerometry, measured 4x/day for 7 days, at baseline and 12 weeks), compared between the 3 treatment groups

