6.1 Screening/Baseline Visit

Depending on state or institutional COVID-19 restrictions at time of screening, baseline visits may be conducted virtually (via video meeting) or in-person. Even when in-person visits are permitted, participants will still be given the option for virtual visits.

For in-person visits, subjects will be seen at one of several UM or UW sites for baseline visit activities, including but not limited to the University of Michigan Taubman Neurology Clinic, Michigan Clinical Research Unit (MCRU), and the UW Medicine Multiple Sclerosis Center.

Informed consent will be obtained by qualified study staff. Inclusion and Exclusion Criteria will be reviewed. For virtual visits, the informed consent will be obtained digitally. See section 7.2.4.

The screening portion of this visit will include confirmation of eligibility via:

- 1) Participant self-report (e.g. FSS, PHQ-3, etc.)
- 2) Demographic information
- 3) Focused medical and surgical history as it relates to multiple sclerosis (subtype, prior disease modifying therapy use, disease duration), fatigue, mood disorders and hepatic issues (for modafinil)
- 4) Medication review

5) Neurologist assessment of eligibility

6) Pregnancy test (For individuals of childbearing age who identify their pregnancy status as unsure)

Eligible subjects will be randomized into one of the 3 study arms & will complete baseline assessments of self-reported fatigue, disability, sleep, exercise, self-efficacy, and other quality of life factors via online Redcap surveys.

6.2 Home monitoring 7-day PRO-Diary application (EMA) – BASELINE AND WEEK 12 ONLY: After completing the above screening/baseline activities, participants will receive instruction on use of the PRO-Diary® accelerometer watch, which the participant will wear during two separate 7-day “home monitoring” periods, at baseline (sent home with watch following baseline visit) and 12 weeks to assess physical activity (objectively measured via accelerometry), AND ecological momentary assessment (EMA) of fatigue intensity, fatigue impact, fatigability (ration of fatigue intensity/accelerometer activity counts), and sleep. See “Assessments” section.

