The 7-day monitoring period at 12 weeks will take place at the end of the study treatment interval; so that the home monitoring takes place before participants have discontinued their Modafinil, the assessment will begin approximately one week before the end of treatment for all treatment arms (i.e., home monitoring will *conclude* around 12 weeks post-treatment initiation).

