Group 2 (Modafinil monotherapy)*: Participants will have the option of completing all REDCap assessments remotely (computer based assessments via weblink which will be provided, or paper forms by mail), or in-person. An internet-connected device will be provided by the study staff member for the participant to complete the REDCap assessments if they choose to complete them during the study visit. Participants will be able to receive drug refill at 8-week either in-person at UMHS (for in-person visit) or in the mail (for virtual visit). Participants will be encouraged to complete the Week 12 REDCap assessment during the final (12th) week of treatment, as close to the end of treatment as possible. For Week 12 home monitoring period, the PROdiary and instructions for completing the monitoring and for returning the PROdiary following the 7-day monitoring period (accompanied by a pre-paid return envelope) will be mailed to participants, so that the materials are delivered to the participant ahead of the start of the 11th week. The study staff member will place a reminder call to the participant on or around the first day of the Week 12 home monitoring period and will answer any questions that participant has about completing the Week 12 home monitoring. Participants will be asked to report number of remaining modafinil pills at the end of the treatment period and can either bring back any unused modafinil to the study personnel to properly dispose of it, or receive the drug destroyer via mail at the end of the 12-week treatment interval to properly dispose of any unused modafinil.

Group 3 (Combination therapy)*:

Participants will have the option of completing all REDCap assessments remotely (computer based assessments via weblink which will be provided, or paper forms by mail), or in-person. An internet-connected device will be provided by the study staff member for the participant to complete the REDCap assessments if they choose to complete them during the study visit. Participants will be able to receive drug refill at 8-week either in-person at UMHS (for in-person visit) or in the mail (for virtual visit).

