4. Home Monitoring Prior to Week 12: The Week 12 PRO-Diary home monitoring data collection will ideally commence 7 days prior to the final day of modafinil administration. A minimum of 3 days of monitoring during the final week of modafinil administration will be acceptable for completion of this data collection, as no monitoring should take place after modafinil has stopped; monitoring will cease following the last day of modafinil treatment even if an entire 7 days of data has not been collected.
5. Week 12 Assessment Window: The Week 12 survey (REDCap) assessment can be completed up to 2 weeks (-14 days) prior to the Week 12 visit, but if possible should be completed within the final week of modafinil treatment, and no later than final day of modafinil administration.

6. Week 24 Assessment Window: A \pm 1-month (\pm 30 days) window around the Week 24 period will be allowed for collection of follow-up data.

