6.7 Treatment Windows

CBT: For participants randomized to receive CBT, treatment will commence as soon after the last day of baseline PRO-Diary monitoring as therapist/participant schedules will allow. Efforts will be made to complete 1 session per week for 8 consecutive weeks (main treatment sessions) followed by 2 approximately every-other-week maintenance sessions (maintenance sessions). However, flexibility in the scheduling of these sessions will allow for, at a minimum, completion of the 8 main treatment sessions within the 12-week treatment period. If needed, scheduling of >1 session/week, but no more than 2 sessions in a 7-day period is allowable to ensure that the full treatment is delivered in the 12-week treatment period. No treatment sessions will be delivered beyond the 12-week treatment period.

Modafinil: For participants randomized to receive modafinil, treatment will commence the day after the last day of baseline PRO-Diary monitoring, and continue for a period of 12 consecutive weeks. For patients receiving combination therapy, Modafinil will start on or before first day of CBT.

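### Section 6.6 item 4 ties Week 12 PRO-Diary monitoring to still taking modafinil, while Section 6.2 ties it to the calendar in all arms; read literally, item 4 leaves early modafinil stoppers without post-baseline EMA data

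*Combined protocol and SAP*

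**What the plan says.** The EMA and fatigability outcomes of Section 2.2.2 come from the PRO-Diary, "measured 4x/day for 7 days, at baseline and 12 weeks". Section 6.2 confirms that there are two wearing periods, "BASELINE AND WEEK 12 ONLY", and the schedule in Section 6.9 shows no PRO-Diary measure at Week 8 or Week 24. Week 12 is therefore the only post-baseline measurement.

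The timing of that measurement is given in two ways.

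- **Calendar anchor.** Section 6.2 starts it about a week before treatment ends, in all arms, and finishes it about 12 weeks after treatment began. Its reason is "so that the home monitoring takes place before participants have discontinued their Modafinil". Section 6.5 mails the watch to every group, "so that the materials are delivered to the participant ahead of the start of the 11th week", and adds a reminder call. Section 6.8 (payment) and the Section 6.9 block "7-day home monitoring (PRO-Diary) measures" attach no condition on being on drug.
- **Drug anchor.** Section 6.6 item 4 sets a floor: "A minimum of 3 days of monitoring during the final week of modafinil administration will be acceptable for completion of this data collection". The reason that it gives for this floor is worded as a prohibition: "as no monitoring should take place after modafinil has stopped; monitoring will cease following the last day of modafinil treatment". It makes no exception for someone who stopped early.

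Section 6.7 has modafinil "continue for a period of 12 consecutive weeks". Section 1.3 encourages participants who choose to stop modafinil to remain in the study until completion, and Section 13 does the same for those withdrawn from it. Section 6.6 has out-of-window assessments recorded as protocol deviations. Section 9.2 plans between-group analyses of the EMA outcomes without saying whether data collected off treatment are used.

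**The concern.** For a participant who takes modafinil for the full 12 weeks, the two anchors give the same days. For one who stops for good in, say, week 5 and stays in the study, they conflict: Section 6.2 calls for monitoring near Week 12, and item 4 says none should take place. Two sites could handle the same participant differently, and both could point to the protocol.

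If item 4 is followed literally, the missing values arise because treatment was stopped, and only in Groups 2 and 3. Group 1 is monitored by the calendar whether or not CBT sessions are still being attended. The comparisons of EMA fatigue intensity, EMA fatigue impact and fatigability would then set everyone still in the study under CBT against only those still on drug in the other two arms. That sits badly with a pragmatic comparison of randomised strategies. The adherence (dose-response) analysis in Aim 3 would also lose, for these outcomes, some of the least adherent participants.

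**Working it through.** The plan gives no figure for these outcomes or for early stopping, so the check is mainly textual. The arithmetic covers timing and an illustration of size.

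**1. Who is affected (Sections 6.5, 6.6, 6.7, 13).** Treatment lasts 12 × 7 = 84 days from Day 1. Week 11 starts on Day 10 × 7 + 1 = 71. The last 7 days are Days 78 to 84. Three on-drug days counted from Day 78 need a last dose on Day 80 or later.

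| Participant in Group 2 or 3 | In-protocol Week 12 EMA value under item 4? |
|---|---|
| At least 3 monitored days on drug | Yes |
| Paused, restarted, and on drug in the final week | Yes |
| Stopped for good about Day 71 to 79, stays in study | Depends on whether monitoring had begun |
| Stopped for good before about Day 71, stays in study | No: the watch comes just before week 11 and nothing provides for monitoring at an earlier unplanned stop |
| Left the study | Missing anyway, not because of item 4 |

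**2. Can another provision fill the gap?** Section 6.6 lets a participant who misses a window complete later assessments, but no PRO-Diary period follows Week 12. Its tolerance of missed EMA prompts concerns prompts within a monitoring period, not the loss of the only post-baseline period.

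**3. Size, as an illustration on assumed values.** Let p be the share of a modafinil arm who stop for good too early to be monitored and stay in the study. Let d be their difference from continuers at Week 12, in SD of the outcome. Neither is in the documents. With 330 enrolled 1:1:1 (Section 4.0), each arm has 330/3 = 110, so p = 5%, 10% and 20% means 5.5, 11 and 22 people per arm.

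Shift of a modafinil arm against CBT = p × d:

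| p | d = 0 | d = 0.33 | d = 0.67 |
|---|---|---|---|
| 5% | 0 | 0.017 | 0.034 |
| 10% | 0 | 0.033 | 0.067 |
| 20% | 0 | 0.066 | 0.134 |

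A negative d reverses the sign. Group 2 against Group 3 shifts only if p or d differs between them. For pooled monotherapy against combination, with p and d equal in both modafinil arms, the shift is about half the tabled value, because only one of the two pooled arms is affected.

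**4. What a mixed model recovers.** With only baseline and Week 12, the remaining shift is p × (d − r × d0), where d0 is the stoppers' baseline difference and r the baseline-to-Week-12 correlation (0.6 assumed):

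- p = 0.20, d = 0.67, d0 = 0: 0.20 × 0.67 = 0.134
- p = 0.20, d = 0.67, d0 = 0.33: 0.20 × (0.67 − 0.198) = 0.094
- p = 0.10, d = 0.33, d0 = 0.33: 0.10 × (0.33 − 0.198) = 0.013

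**5. Scale.** With 100 per arm the standard error of a two-arm difference is √(2/100) = 0.14 SD, or 0.14 × √(1 − 0.6²) = 0.11 SD after baseline adjustment at r = 0.6. The planning effect for the MFIS in Section 9.1, used only as a yardstick, is 5/12 = 0.42 SD.

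**The case against.** The strongest reply is that item 4 is a scheduling clause. It sits among assessment windows, its reason is the one given in Section 6.2, and Section 6.7 fixes a 12-week course. It names no arm although Group 1 takes no modafinil, which suggests that the stop it means is the scheduled end of treatment. On that reading Section 6.2 already supplies the calendar window and only one clause is out of line. This is probably the intent, and it stands. But item 4 does not say so, and its wording is categorical.

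It can also be said that monitoring done off drug is not forbidden data: Section 6.6 records out-of-window assessments as deviations and nothing excludes them from analysis. That stands too. It means that a literal reading leaves no in-protocol value, not that no value can exist. It still leaves collection to local judgement and use to the analyst.

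A reader might infer that Sections 1.3 and 13 contradict item 4. They do not: they encourage staying in the study, for safety monitoring and observation, and do not mention the PRO-Diary. The conflict is between item 4 and Section 6.2. A reader might also infer bias in the primary analysis, because items 3 and 5 tie the Week 8 and Week 12 windows to modafinil in similar language. The documents do not support that. The MFIS is a survey also taken at Weeks 8 and 24, the wording reads as timing guidance, and Section 6.6 lets participants who miss a window continue. Those items need only the same clarification.

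Finally, every value of p, d, d0 and r is assumed. Self-adjustment of dose and the restart provision may keep permanent stopping low. At p = 5% the shift is at most about 0.3 of a standard error (0.034/0.11). Only the 20% and 0.67 SD corner reaches about one.

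**Conclusion.** The point holds as an internal conflict with a practical consequence. Item 4 and Section 6.2 agree only for participants who complete 12 weeks of modafinil. Followed literally, item 4 produces treatment-related missing values in Groups 2 and 3, and not in Group 1, for the Section 2.2.2 outcomes only. Section 9.2 does not settle how off-treatment monitoring data are handled.

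Size and direction are unknown because the documents give no stop rate and no information on how stoppers differ. On the assumed ranges the shift against CBT lies between zero and about 0.13 SD in either direction. It is small if few participants both stop and stay, and zero if stoppers do not differ from continuers. The upper figure should not be read as an estimate of bias. The change is still worth making, because Week 12 monitoring that was not collected cannot be recovered, while an on-treatment analysis can always be drawn from complete data.

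**What to change.** 1. Reconcile Section 6.6 item 4 with Section 6.2. Define the Week 12 home-monitoring window in days from Day 1, the same in all three arms, and collect it whether or not study treatment is still being taken. Keep completion before the final scheduled dose as a timing target for those still on drug.
2. Add a phrase to items 3 and 5 that their references to modafinil do not bar survey data from early stoppers.
3. State in Section 9.2 that the Section 2.2.2 outcomes are analysed as randomised, including monitoring done off treatment, with an on-treatment sensitivity analysis. Whether off-treatment data enter the main analysis is a choice of estimand, so it should be stated rather than left to be inferred from a window rule.

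The cost is a few lines of protocol text. Watches are already mailed to every arm under Section 6.5. The drawback is some dilution of the estimates by off-drug data, which the sensitivity analysis would show. No dosing or stopping rule changes.
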